Appendix J: Standard operating procedures

The MobiliseMe study: Testing different smartphone activities to help improve young people's mental health

Trial Management Group

Version 1 (25th October 2021)

Procedures for eliciting reports of and for recording and reporting adverse event and intercurrent illnesses.

Adverse Events and Serious Adverse Events

For this current trial, an adverse event (AE) is defined as any untoward medical or clinical occurrence in a participant without regard to the possibility of a causal relationship. All AEs will be collected after a participant has consented and enrolled into the trial. AEs may include severe suicidal ideation as reported on baseline, primary or secondary endpoint online self-report assessment. Severe suicidal ideation will be defined as self-reports of suicidal thoughts or thoughts of self-harm More than half the days or Nearly every day, indicated by a score of ≥ 2 on item-9 of the PHQ-9. AEs also include severe depressive symptoms reported by participants at the final assessment (secondary endpoint) before trial ends. Severe depressive symptoms are indicated by a total score ≥ 20 on the Patient Health Questionnaire-9 at secondary endpoint assessment (i.e., 4-months post-baseline). Finally, AE also include mental health related hospitalisation reported at primary or secondary endpoint or disclosed in any other study procedures (e.g. call back phone calls, participant emails).

A serious adverse event (SAE) for this trial is defined as any untoward occurrence that involves hospitalization or death (suicide or otherwise) without regard to the possibility of a casual relationship.

Adverse Reactions (AR) are considered untoward and unintended responses to the trial intervention related to any intervention procedures. AR may include self-identified deterioration in mental health due to study activities reported by participants at primary or secondary endpoints.

Reporting Adverse Events

The trial will maintain a record of any reported adverse events or serious adverse events. A summary of adverse events will be reported to the trial's qualified expert (as named in Section 1). A summary of serious adverse events will be reported annually to the UNSW sponsors delegate and UNSW ethics committee.

Due to the low-risk nature of this trial, a formal Data and Safety Monitoring Committee (DSMC) will not be convened. In lieu of the of the DMSC, a Trial Management Group (TMG) will be employed for all monitoring and reporting. Adverse events and serious adverse events will be reported to the Trial Management Group (TMG) when they meet.

Any suspected unexpected serious adverse reactions (SUSAR) will be reported immediately to the Sponsors' independent expert. If the independent expert classifies/confirms the report as an unexpected serious adverse reaction, they will report this immediately to the coordinating principal investigator (CPI). The CPI will report the SUSAR to the UNSW Sponsors' delegate as soon as possible and within 7 days of being made aware of the SUSAR.

If a significant safety issue (SSI) arises during the trial (e.g., any issue that could adversely affect the safety of participants or materially impact on the continued ethical acceptability or conduct of the trial), that requires an urgent safety measure (e.g., any action taken to eliminate an immediate hazard to a participants health), this will be documented and reported to the UNSW ethics committee and the UNSW sponsors delegate as soon as possible and within 7 days.

In accordance with UNSW requirements, the Chief Investigator will also notify the UNSW Sponsor's delegate of:

- Protocol Deviation reports outlined in the UNSW Research Misconduct Procedure.

- Any serious breach of Good Clinical Practice, the clinical trial protocol, the clinical trial standard operating procedures, or the human ethics approval that is likely to affect to a significant degree the safety or rights of participants or the reliability and robustness of the data generated in the clinical trial.
- Safety Reports relating to the continuation, suspension, or discontinuation of the clinical trial for safety reasons as they arise.
- Participant complaints or concerns received in relation to the conduct of the research.
- Any significant modifications to the clinical trial that are likely to affect to a significant degree the safety or rights of participants or the reliability and robustness of the data generated in the clinical trial.
- Amendments to clinical trial research agreements or service level agreements.
- Revisions to regulatory requirements including correspondence with the Therapeutic Goods Administration, clinical trial registries or the FDA.

Procedure for the type and duration of the follow-up of subjects after adverse events

The current trial will recruit participants from a clinical population, it's expected that feelings of anxiety and/or depression, and suicidal thoughts or thoughts of self-harm will be common. Included at the end of each mental health assessment at (baseline, primary or secondary endpoint) are suggested resources and contact details for services, should participants become distressed and need assistance. These services include Lifeline, Beyond Blue, and Kids Helpline as well as a range of resources and support from the Black Dog Institutes website. Participants that experience an AE related to severe suicide ideation or severe depressive symptom will be offered a follow-up call from a Clinical Psychologist. The Clinical Psychologist will conduct a brief risk assessment over the phone to determine the level of risk. If determined to be at risk, the participant will be advised to contact an appropriate service (e.g., a GP, the BDI Psychology Clinic, Mental Health Hotline). If the risk of harm is deemed significant enough to break confidentiality, or the participant requests it, their parents will be contacted by mobile telephone within an additional two working days. Referral suggestions will be provided.

Procedure for accounting for missing, unused, and spurious data

All data will be collected via online surveys, rather than pencil-and-paper responses, reducing the amount of missing data or errors within the data set. To maintain data integrity frequency tables of all variables (including time and date information) will be collected and checked to ensure that scale items have only legal values. These legal values will also be checked for coherency (i.e., do end times/dates occur after corresponding 'start' time/dates).

Any missing items will be flagged with a value that cannot be confused as a legal value. Additionally, a present/absent indicator variable will be created for each data collection timepoint to track missing data due to participant absence. For partially answered inventories, respondents that answer at least 50% of items on a scale and still have a valid score will be allowed (Bell & Fairclough, 2014). Respondents that have less than 50% of items on scale completed will be assigned as missing values. The research team will be guided by the trial statistician in data analysis.

Procedures for reporting any deviation(s) from the original statistical plan (any deviation(s) from the original statistical plan should be described and justified in protocol and/or in the final report, as appropriate)

Any deviation for the original statistical plan will be submitted to the University of New South Wales HREC for approval before implementation

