This study will utilise a three-arm randomised controlled trial, conducted entirely online via the Black Dog Institute Research Engine. Data will be assessed at baseline, primary endpoint (6-weeks post-baseline) and secondary endpoint (4-months post-baseline). This methodology is appropriate to meet the research aims because RCTs are considered to provide the most reliable evidence on the effectiveness of interventions because the processes used during the conduct of this type of trial minimise the risk of confounding factors influencing the results. Because of this, the findings generated by RCTs are likely to be closer to the true effect than the findings generated by other research methods (Akobeng, 2005).

Randomisation will be carried out according to the International Council for Harmonisation (ICH) guidelines. Randomisation to one of the three trial arms will be conducted immediately after completion of the baseline assessment using a computerised randomisation procedure within the Black Dog Institute Research Engine. Stratified randomisation approach with a block size of 6 (1:1 ratio) will be used to ensure balance across the conditions in terms of age (12 to 14 years vs. 15 to 17 years), ~~gender (male vs. female)~~, and symptom severity (mild [as determined by a total score of 9 or less on the PHQ-A] vs moderate to moderately-severe [as determined by a total score of 10 or more on the PHQ-A]). Allocation will be fully automatic, with no interference from the research team.

Blinding – Participants: All study materials will refer to the interventions being examined as “smartphone activities and information for your mental health”. While participants will be aware of which smartphone activity they will be required to use (due to the PICF and instructions for use provided), they will not be directly informed of their condition allocation (i.e., intervention 1 vs. intervention 2 vs. control).

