The study flow is outlined in Appendix K. Upon the provision of full consent, participants will be invited to complete the baseline assessment via an automated email/SMS invitation generated by the Black Dog Institute Research Engine. The outcome measures assessed at baseline are outlined in Appendix D. The baseline assessment is entirely self-report. It will take approximately 20 minutes to complete, and can be completed on any Internet-enabled device. Participants will have 7 days to complete the baseline assessment (from invitation date) and will receive two reminders to complete the assessment (sent on day 3 and day 5). Participants who fail to complete the baseline assessment within 7 days will be withdrawn from the study.

Once baseline is completed, participants will be automatically randomised by the Black Dog Institute Research Engine to one of three trial arms (outlined in Section 10.1). Upon randomisation, participants will be presented with a webpage that provides them with individual instructions and installation advice on the requirements for their trial arm. Participants allocated to Trial Arms 1 and 2 who fail to download the ClearlyMe app within 7 days of randomisation will be sent an email and SMS reminder to download the app.

The study intervention period is 6-weeks, with the primary endpoint assessed at 6-weeks post-baseline. At primary endpoint, participants will be invited to complete the primary endpoint assessment via an automated email/SMS invitation generated by the Black Dog Institute Research Engine. The outcome measures assessed at primary endpoint are outlined in Appendix E. The primary endpoint assessment is entirely self-report. It will take approximately 20 minutes to complete and can be completed on any Internet-enabled device. Participants will have 7 days to complete the primary endpoint assessment (from invitation date) and will receive two reminders to complete the assessment (sent day 3 and day 5). During the intervention

period, the study will also collect data on participants' use of the interventions. This measurement is outlined in Appendix D under 'Intervention Use'.

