11.2 Adverse Events or Adverse Reactions

Adverse events (AE) are considered any untoward medical occurrence in a patient or clinical trial participant administered the intervention, which does not necessarily have a causal relationship with this treatment.

Adverse Reactions (AR) are considered untoward and unintended responses to the trial intervention related to any intervention procedures.

AEs and ARs are assessed using the safety monitoring flow chart. Those classified as "not serious" are assessed by the qualified physician/medical expert specified in section 2 of the protocol. The Qualified Physician cannot delegate this responsibility to other research personnel.

Adverse event reports must be reported to the Coordinating Principal Investigator within 48 hours of the research team being made aware. All adverse event reports must be recorded in the [UNSW Safety Monitoring Register Template](#).

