- Frequent, current suicidal ideation (i.e., thoughts of death or of harming oneself, score greater than 2 on item 9) detected through the self-report Patient Health Questionnaire-9 at primary or secondary endpoint.
- Severe depressive symptoms detected at final study assessment (i.e., secondary endpoint: 4-months post-baseline) through the self-report Patient Health Questionnaire-9.

- Mental health related hospitalisation reported at primary or secondary endpoint or disclosed in any other study procedures (e.g. call back phone calls, participant emails).
- Self-identified deterioration in mental health due to study activities reported by participants at primary or secondary endpoints.

Stopping guidelines

The primary charge of the TMG is to monitor the study for participant safety. As such, the TMG may recommend pausing or terminating the trial if they have concerns for participant safety, based on (but not limited to) a higher than anticipated rate for one or more of the primary endpoints.

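### Appendix J and Section 11.1 class suicidal ideation at the pre-randomisation baseline as an adverse event, against Section 11.2 and Appendix I, and later scores count without reference to baseline

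*Protocol*

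**What the plan says.** **Rules that include baseline.** Appendix J (Adverse Events and Serious Adverse Events) says "AEs may include severe suicidal ideation as reported on baseline, primary or secondary endpoint online self-report assessment", with severe ideation "indicated by a score of ≥ 2 on item-9 of the PHQ-9". Collection starts early: "All AEs will be collected after a participant has consented and enrolled into the trial". The Section 11.1 table of known adverse effects also names baseline alongside the primary and secondary endpoints.

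**Rules that do not fit this.** Section 11.2 defines an adverse event as "any untoward medical occurrence in a patient or clinical trial participant administered the intervention". Appendix I (Safety analyses) sets the ideation safety endpoint as ideation "detected through the self-report Patient Health Questionnaire-9 at primary or secondary endpoint", without baseline.

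**Order of events.** Section 7: "Randomisation to one of the three trial arms will be conducted immediately after completion of the baseline assessment". Section 10 agrees: "Once baseline is completed, participants will be automatically randomised by the Black Dog Institute Research Engine to one of three trial arms".

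**Causality.** Appendices I and J define an adverse event as "any untoward medical or clinical occurrence in a participant without regard to the possibility of a causal relationship".

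**The concern.** Item 9, as worded in Section 11.1, asks about the previous two weeks. At baseline it therefore describes the participant before allocation. Classing that answer as an adverse event puts pre-treatment status in the same register as events that could follow an intervention, and contradicts the protocol's own definition in Section 11.2.

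The second part concerns the later assessments. A score at or above the cut-off at 6 weeks or 4 months counts whether or not it was already there at baseline. Unchanged ideation and ideation that began after randomisation are then the same kind of record, although only the second is evidence of deterioration.

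These records are used. Events go into the safety monitoring template, which the Trial Management Group reviews after each of the three assessments (Appendix I). The register goes to the sponsor's delegate every year (Section 11.9). Appendix J says that no separate data and safety monitoring committee will be convened. The stopping guideline in Appendix I looks at whether event rates exceed expectation, and a rate that includes persisting ideation cannot by itself show whether participants have got worse.

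**Working it through.** The protocol gives no event rate for ideation, so there is no planned figure to reproduce. The check has three parts.

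**1. The rules side by side**

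| Place | Baseline counted? | Later score tied to baseline? |
|---|---|---|
| Section 11.1 table | yes | no |
| Appendix J | yes | no |
| Section 11.2 definition | no (requires the intervention) | not addressed |
| Appendix I safety endpoint | no | no |

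The most records one participant with persisting ideation can give is 3 under Appendix J (1 of them before randomisation) and 2 at the Appendix I time points. Under a rule that counts only new or worsened scores after randomisation it is 0. Appendix J does not say whether persisting ideation is one event or several, so the count of 3 is an inference.

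**2. Can a randomised participant have such a baseline score?** Section 9.2 excludes an item 9 score of 2 or more, but at screening. Section 9.5 allows 14 days for parental consent and then 7 days for baseline, 14 + 7 = 21 days or so. Section 10 randomises automatically once baseline is complete and states no further exclusion. Section 11.1 provides for such scores at baseline. So it can happen, in participants who reach the cut-off within that interval.

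**3. How much could it matter?** The inputs are:
- response at 6 weeks 0.8, from the 20% attrition in Section 8;
- response at 4 months *a* = 0.6 to 0.8 (assumed);
- *r* = baseline prevalence divided by follow-up prevalence (assumed; taken relative to the unaffected arm in the ratio below);
- *w* = 0.8 + *a*.

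The share of ideation records made at baseline is *r*/(*r* + *w*). If follow-up ideation truly doubles in one arm and all three assessments are pooled, the ratio of records between arms is (*r* + 2*w*)/(*r* + *w*).

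| *r* | *a* | Baseline share | Pooled ratio (truth 2.0) |
|---|---|---|---|
| 0.1 | 0.8 | 0.1/1.7 = 6% | 3.3/1.7 = 1.94 |
| 0.5 | 0.8 | 0.5/2.1 = 24% | 3.7/2.1 = 1.76 |
| 1 | 0.8 | 1/2.6 = 38% | 4.2/2.6 = 1.62 |
| 2 | 0.6 | 2/3.4 = 59% | 4.8/3.4 = 1.41 |

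The difference between arms is (*r* + 2*w*) − (*r* + *w*) = *w*, which does not depend on *r*. Baseline records therefore leave the expected difference unchanged.

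For persisting ideation at the Appendix I time points, let *b* be baseline prevalence, *q* the proportion still at or above the cut-off at each later assessment, and *e* = 3% new onset at each (all assumed, with equal response at both). The persisting share is *bq*/(*bq* + (1 − *b*)*e*):
- *b* = 1%, *q* = 30%: 0.003/(0.003 + 0.0297) = 9%;
- *b* = 10%, *q* = 70%: 0.07/(0.07 + 0.027) = 72%.

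The width of this range shows how little can be said without a prevalence.

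**The case against.** The strongest defence is that the endpoint used for monitoring already leaves baseline out. Appendix I restricts the ideation endpoint to the two later assessments, and its stopping guideline refers to the endpoints listed there. Appendix J is an operating procedure for recording events. This stands. A reader might infer that the plan would hide a harmful arm behind a diluted ratio, but no section proposes pooling the three assessments into one comparison between arms. Section 11.1 has contacts logged with dates, and baseline records can be separated.

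A reader might also infer that baseline ideation is being recorded as harm caused by the trial. The appendices define adverse events without regard to cause, and Appendix J keeps adverse reactions as a separate category. Collecting events from consent is a legitimate choice. Section 11.1 does list these events as known adverse effects, but that supports a complaint about labelling, not about attribution.

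The screening exclusion also counts in the plan's favour. Section 9.2 removes this same score, and also serious suicidal ideation or an attempt in the past month, so baseline cases may be few. At *r* = 0.1 the dilution is slight. Against that, Appendix J expects suicidal thoughts to be common in this population.

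Finally, a by-arm table of new-onset and persisting ideation could sit in a statistical analysis plan that is not shown, so it cannot be said that the two are never separated. What the defence does not answer is that the protocol itself fixes what counts as an adverse event and does so in two incompatible ways.

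**Conclusion.** The point holds as a contradiction in the protocol's adverse event rules. Section 11.1 and Appendix J include the pre-randomisation baseline, while Section 11.2 and the Appendix I endpoint do not. As written, pre-treatment ideation can enter the register at up to three assessments (inferred) and the Appendix I endpoint at up to two.

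The size is unknown. Under the assumptions above, baseline records make up about 6% of ideation records if baseline prevalence is 0.1 times follow-up prevalence, and 59% if it is twice. The lower figure is not a floor, since the share tends to zero as baseline cases become rare. The effect is on total counts, and on a ratio only if someone pools the assessments; the comparison between arms by difference is not biased. The missing link to the baseline score is the part that reaches the monitored endpoint. This is worth correcting because it concerns a main safety signal in a trial of minors and the correction is cheap, not because a distorted comparison has been shown.

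**What to change.** Reconcile Section 11.1, Section 11.2, Appendix I and Appendix J so that they agree on whether a baseline item 9 score is an adverse event and from what point events are counted. In doing so:

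- Keep recording from consent, and leave the baseline pop-up message and call-back offer exactly as written.
- Flag a baseline item 9 score of 2 or more as pre-randomisation baseline status, and leave it out of by-arm adverse event counts.
- At 6 weeks and 4 months, report ideation by arm as new-onset (below the cut-off at baseline, at or above it later) and persisting (at or above it at both), each over participants assessed, next to the full count.
- Use one cut-off throughout. Appendix I words it as greater than 2 and Appendix J as 2 or more, and these too must be reconciled before the split can be derived.

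Moving the start of all adverse event recording to randomisation is not needed, and would lose events between consent and allocation that Appendix J deliberately collects.

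The cost is a wording change in the sections named and one derived variable from data already collected. New-onset counts will be smaller and so less precise, which is why the full count should stay beside them.
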